7.1. Duration

Study subjects will be enrolled and will complete enrollment/baseline requirements to determine eligibility. Subjects that do not qualify for the study prior to the first PTNM therapy session will be exited from the study. All enrolled subjects that qualify for the study (meet all inclusion and no exclusion) will receive 12 PTNM therapy sessions, each approximately 1 week apart, prior to completing the final study visit. The visits are expected to occur over a 14 week period.

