9.2. Subject Enrollment

Subjects are considered enrolled at the time the study-specific ICF is signed. Each subject must meet all of the inclusion criteria and no exclusion criteria to be eligible to participate in this study. Any subject meeting an exclusion criterion will be excluded from study participation.

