12.1. Definitions/Classifications

Any adverse event meeting the definition of: serious, device related, and/or procedure related as well as all device deficiencies will be considered reportable for this study. Adverse events and device deficiencies are defined as follows:

Term	General
Adverse Event (AE)	Any untoward medical occurrence, unintended disease or injury, or untoward clinical signs (including abnormal laboratory findings) in subjects, users or other persons, whether or not related to the medical device under investigation.
Adverse Device Effect (ADE)*	Adverse event related to the use of the medical device under investigation.
Device Deficiency (DD)*	Inadequacy of a medical device with respect to its identity, quality, durability, reliability, safety or performance. Device deficiencies include malfunctions, misuse or use errors, and inadequate labeling. 
▪ Malfunctions: Failure of the medical device under investigation to perform in accordance with its intended purpose when used in accordance with the instructions for use or Clinical Investigational Plan (CIP)▪ Use Error: Act or omission of an act that results in a different medical device response than intended by the manufacturer or expected by the user

Confidential

SERIOUSNESS	
Serious Adverse Event (SAE)*	
An adverse event that
 
 a) led to a death, b) led to a serious deterioration in the health of the subject, that either resulted in: 
 1. a life-threatening illness or injury, or 2. a permanent impairment of a body structure or a body function, or 3. in-patient or prolonged hospitalization, or 4. medical or surgical intervention to prevent life threatening illness or injury or permanent impairment to a body structure or a body function. c) led to fetal distress, foetal death or a congenital abnormality or birth defect. 
Note: A planned hospitalization for pre-existing condition, or a procedure required by the CIP, without a serious deterioration in health, is not considered to be a serious adverse event.

Serious Adverse Device Effect (SADE)*	Adverse device effect that resulted in any of the consequences characteristic of a serious adverse event
Unexpected Serious Adverse Device Effect (USADE)*	Serious adverse device effect which by its nature, incidence, severity or outcome has not been identified.
RELATEDNESS	

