14.5. Additional Measures

Additional measures include:

- Incidence of device-related and therapy-related adverse events
- Nocturia / Nighttime voiding frequency
- Urgency including the Urgency Perception Scale (UPS)
- Patient-reported Outcomes:
 - Self-Assessment Goal Achievement Questionnaire (SAGA)
 - Patient Perception of Bladder Condition (PPBC)
 - Patient Global Impression of Improvement (PGI-I)

Nocturia, nighttime voiding frequency and urgency are collected through voiding diaries and patient reported outcomes. Reductions in nocturia, nighttime voiding frequency and urgency from baseline will be summarized by the PTNM session when the data is collected.

Additional quality of life measures including PPBC, UPS, PGI-I and SAGA are collected in this study. These data will be summarized by the PTNM session when data is collected.

Confidential

Reportable adverse events will be summarized for all subjects who receive the therapy.

Fecal incontinence diaries will be collected for subjects with dual incontinence. No analysis is pre-specified for dual incontinence data. The intent of collecting this information is to inform future study designs.

15. Ethics

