5.2. Subject Enrollment

Subjects are considered enrolled at the time the study-specific Informed Consent Form (ICF) is signed. Each subject must meet all of the inclusion criteria and no exclusion criteria to be eligible to participate in this study. Any subject meeting an exclusion criterion will be excluded from study participation.

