7.9.3. Additional Measures

7.9.3.1. Incidence of device-related or therapy/procedure-related adverse events

Objective:

To summarize the device-related or therapy/procedure-related adverse events for all subjects who receive the PTNM therapy.

Endpoint definition

Device-related and therapy/procedure-related adverse events are defined as possible, probable and causal relationship to study procedure, NURO external neurostimulator, therapy session kit, and stimulation as reported on the event case report form (CRF). The sponsor assessment on the event is documented in the Medtronic Use Only CRFs. When there are differences in event CRF reporting and MUO CRFs, both will be reported in the final report, and the events summaries will be based on more conservative approach: for example, if it is reported as device related and not assessed as such in MUO CRF, the event will be counted as device related in event summaries.

Data collection and analysis methods

Device-related and therapy/procedure-related adverse events will be summarized by MedDRA preferred terms for all qualified subjects who receive the PTNM therapy. Number of subjects and percent of

subjects in each preferred term will be reported. These events will be further summarized by serious events and non-serious events.

Determination of subjects for analysis

All qualified subjects who receive the PTNM therapy will be included in the analysis.

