7.10. Safety Evaluation

In the study, reportable Adverse Events are collected. All serious, device related, therapy/procedure related and all device deficiencies are considered as reportable for this study. The sponsor assessment is documented in the Medtronic Use Only (MUO) CRFs. When there are differences in event CRF reporting and MUO CRFs, both will be reported in the final report, and the events summaries will be based on more conservative approach: for example, if it is reported as device related and not assessed as such in MUO CRF, the event will be counted as device related in event summaries.

Incidence of device-related and therapy/procedure-related adverse events will be summarized as detailed in Section [7.9.3](#).

Serious AEs (SAEs), regardless of device-related, therapy/procedure-related or not, will also be summarized for all enrolled subjects.

Device Deficiency will be summarized for qualified subjects who receive PTNM therapy. Additionally, Narratives of SADEs (Serious Adverse Device Effects) will be provided.

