7.11. Changes to Planned Analysis

There are no changes to planned analyses as specified in the protocol.

8. Validation Requirements

Statistical programming code for programming code that affects the result of the main analysis for the primary objective as specified in Section [7.9.1](#) will be validated using Level I validation (peer reviewer independently programs output and then compares the output with that generated by the original Statistical Programmer). Programming code that affects the result of the main analysis for the secondary objectives as specified in Section [7.9.2](#) will be validated using Level II validation (peer reviewer reviews the code; where appropriate, performs manual calculations or simple programming checks to verify the output). In addition, those main analyses that are planned for publication are validated with Level II

validation. Level III validation (original Statistical Programmer performs a visual inspection of the code and output to confirm functionality) may be used for any previously validated program where only minor/administrative changes were made (eg, change the location of the data directory).

9. References

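### SAP 7.10 summarises all-cause SAEs only for all consented subjects, so the summary in treated subjects that protocol 14.5 calls for is missing, and SAP 7.11 declares no change

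*SAP*

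**What the plan says.** On all-cause serious events, SAP 7.10 reads: "Serious AEs (SAEs), regardless of device-related, therapy/procedure-related or not, will also be summarized for all enrolled subjects". The SAP fixes what enrolled means in section 5.2: "Subjects are considered enrolled at the time the study-specific Informed Consent Form (ICF) is signed". Protocol 9.2 gives the same definition.

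Enrolment comes before qualification. Protocol 7.1 says: "Subjects that do not qualify for the study prior to the first PTNM therapy session will be exited from the study". The enrollment/baseline procedures in protocol section 10 place the qualifying 3-day diary after consent.

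Protocol 14.5 sets a different population for safety reporting: "Reportable adverse events will be summarized for all subjects who receive the therapy". Protocol 12.1 defines what is reportable: "Any adverse event meeting the definition of: serious, device related, and/or procedure related as well as all device deficiencies will be considered reportable". A serious event is therefore reportable whatever its cause.

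For events related to the device, therapy or procedure, SAP 7.9.3.1 uses treated subjects: "All qualified subjects who receive the PTNM therapy will be included in the analysis". SAP 7.10 uses the same population for device deficiencies. SAP 7.11 closes with: "There are no changes to planned analyses as specified in the protocol".

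**The concern.** The SAE summary in the SAP is built on a population that is wider than the treated one by every consented subject who never reached session 1. Those subjects have no device exposure. They are observed only from consent to exit, against roughly 14 weeks for a treated subject. Events before the first session are also pooled with events after it, because adverse event review begins at the enrollment/baseline visit (protocol Table 1-1).

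This matters because of what the study collects. Non-serious events unrelated to device or procedure are not reportable, so the all-cause SAE summary is the only adverse-event summary that does not rest on a relatedness judgement. The investigator makes that judgement and a sponsor medical monitor reviews it; there is no Clinical Events Committee or Data Monitoring Committee (protocol section 13). A reader who wants to know how many PTNM-treated subjects had a serious event of any cause should be able to find that figure, and the SAP plans no table that gives it. The all-enrolled summary would also sit beside related-event percentages and a baseline table (SAP 7.6) that use qualified, treated subjects.

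**Working it through.** **Populations side by side**

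| Summary | Source | Population |
|---|---|---|
| Reportable adverse events, including all SAEs | Protocol 14.5 with 12.1 | Subjects who receive the therapy |
| Related adverse events, split by seriousness | SAP 7.9.3.1 | Qualified and treated |
| Device deficiencies | SAP 7.10 | Qualified and treated |
| All-cause SAEs | SAP 7.10 | All enrolled (consented) |

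1. Enrolled means consent signed (protocol 9.2, SAP 5.2).
2. Subjects can be enrolled and never treated: those who fail the diary are exited before session 1 (protocol 7.1 and section 10), as are those who start an OAB medication before session 1 (protocol 10.5).
3. All enrolled is therefore larger than all treated whenever there is at least one such exit.
4. Serious events are reportable regardless of cause, so protocol 14.5 covers them and assigns them to treated subjects.
5. The treated-subject safety summaries in the SAP cover only related events and device deficiencies. None covers SAEs of any cause.
6. SAP 7.11 records no change from the protocol.

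**Size of a possible dilution**

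The documents state no SAE rate, screen-failure count or safety denominator, so there is no planned figure to reproduce. The following is an illustration.

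Inputs:
- T = 120 treated. The protocol synopsis gives up to 120 consented and qualified subjects; treating all 120 is an assumption.
- k = 5 treated subjects with an SAE (assumed).
- s = share of enrolled subjects never treated, 10% to 40% (assumed).
- No SAEs in untreated subjects (assumed).

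Formulas: enrolled N = T / (1 − s). Treated rate = k / T. Enrolled rate = k / N = (k / T) × (1 − s).

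Treated rate: 5 / 120 = 4.2%.

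| s | N | Enrolled rate | Ratio to treated rate |
|---|---|---|---|
| 10% | 120 / 0.9 ≈ 133 | 5 / 133 = 3.8% | 0.90 |
| 20% | 120 / 0.8 = 150 | 5 / 150 = 3.3% | 0.80 |
| 40% | 120 / 0.6 = 200 | 5 / 200 = 2.5% | 0.60 |

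The dilution disappears if untreated subjects have SAEs at the treated rate. At s = 20% there are 150 − 120 = 30 untreated subjects, so this would need 30 × 5 / 120 = 1.25 of them to have an SAE. Their shorter observation makes that unlikely, though not impossible.

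**The case against.** The strongest reply has four parts.

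*The SAP names no rate.* SAP 7.10 says only that SAEs will be summarised, whereas SAP 7.9.3.1 asks explicitly for the number and percent of subjects. A reader might infer that the plan is committed to a diluted SAE incidence. The text does not support that: dilution arises only if a percentage is put on the enrolled denominator. This part stands.

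*The enrolled summary is an addition.* The word also in SAP 7.10, together with the statement in 7.11, could mean that the protocol 14.5 summary is kept and a wider one added. This fails in practice. A programmer working from the SAP would produce treated-subject tables for related events and device deficiencies, and no all-cause SAE table in treated subjects.

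*Counting SAEs from consent is proper.* It accounts for every serious event collected, and a treated-only summary alone would leave some out. This stands. The fault is that the pooled summary is the only one offered.

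*Little depends on it.* Related events, split by seriousness, are already on the treated population, with the more conservative of the investigator and sponsor assessments used, and serious adverse device effects get narratives. No test, threshold or stopping rule uses the all-cause figure. In the illustration, the exact 95% interval for 5/120 runs from 1.4% to 9.5% and contains all the diluted values. This limits the weight of the point. Sampling uncertainty does not, however, justify the choice of denominator.

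Two further readings go too far. A reader might take all-cause SAEs to be the only safety figure free of a relatedness judgement, but device deficiencies also need none. A reader might also think that protocol 14.5 requires onset on or after session 1. It sets the population only and gives no onset cut-off.

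**Conclusion.** The point holds as a gap in descriptive safety reporting and an undeclared difference between the two documents. The absence of an all-cause SAE summary in treated subjects follows from the text alone and needs no assumption.

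The numerical effect is conditional. It requires that a percentage be reported on the enrolled denominator and that untreated subjects have few or no SAEs. With none, the figure is (1 − s) times the treated rate, a relative understatement of 10% to 40% over the assumed range of s. The true s is not in the documents, so the size cannot be fixed; the likely direction is downward. Neither the related serious events in SAP 7.9.3.1 nor any efficacy analysis is affected. The change is worth making because it is specific and close to free.

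**What to change.** In SAP 7.10, add an all-cause SAE summary (number and percent of subjects, number of events) for subjects who receive at least one PTNM session. This brings the SAP into line with the protocol 14.5 population.

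As a further step that goes beyond the protocol, show separately the SAEs with onset before session 1 and the SAEs in subjects who were never treated. No event is then lost, and none is attributed to a period without exposure.

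If the all-enrolled summary is kept, record it in SAP 7.11 as an addition to the protocol analysis.

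The cost is a short edit to the SAP and one extra table. No new data are needed. The reported SAE percentage may be slightly less favourable.

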7.11. Changes to Planned Analysis

There are no changes to planned analyses as specified in the protocol.

8. Validation Requirements

Statistical programming code for programming code that affects the result of the main analysis for the primary objective as specified in Section [7.9.1](#) will be validated using Level I validation (peer reviewer independently programs output and then compares the output with that generated by the original Statistical Programmer). Programming code that affects the result of the main analysis for the secondary objectives as specified in Section [7.9.2](#) will be validated using Level II validation (peer reviewer reviews the code; where appropriate, performs manual calculations or simple programming checks to verify the output). In addition, those main analyses that are planned for publication are validated with Level II

validation. Level III validation (original Statistical Programmer performs a visual inspection of the code and output to confirm functionality) may be used for any previously validated program where only minor/administrative changes were made (eg, change the location of the data directory).

9. References

